7.6 Safety Analysis

The safety analysis will be based on the Safety population (Section 4.1) and will be presented by disease cohort (MM and solid tumor) and overall.

This analysis will be focused on assessing the extent of all reported Grades 3 and 4 adverse events (AEs), all reported peripheral neuropathy AEs (Grades 1-4), all serious adverse events (SAEs), and Grades 1-4 AEs leading to either a missed carfilzomib dose, carfilzomib dose reduction, or discontinuation.

The analysis will remain descriptive in nature.

7.6.1 Adverse Events (AEs)

Treatment emergent adverse events (TEAEs) are defined as AEs that start on or after the first administration of study drug and within 30 days of the last infusion of study treatment. An AE that is present before the first administration of study treatment and subsequently worsens in severity during treatment is also considered to be treatment emergent.

Missing and partially missing AE start dates will be imputed according to the specifications described in Section 7.7.2 of the SAP. Each reported AE term will be mapped to a preferred term (PT) and a system organ class (SOC) using the Medical Dictionary for Regulatory Activities (MedDRA, version 8.1).

Adverse events will be summarized based on the number and percentage of subjects experiencing events by MedDRA SOC and PT. The denominator for the percentage will be based on the number of subjects at risk (i.e., those that received at least one dose of

carfilzomib). The causal relationship of the AE to the study drug will be judged by the investigator as none, unlikely, possible, or probable.

A subject reporting the same AE more than once will be counted only once when calculating 1) within a given system organ class, and 2) within a given system organ class and preferred term combination. For such cases, the maximum National Cancer Institute (NCI; US)-Common Terminology Criteria for Adverse Events (CTCAE, Version 3) toxicity grade and strongest causal relationship to study treatment for the event will be used in the incidence calculations. AEs will also be summarized by severity and by relationship to carfilzomib.

Tabular summaries of the following AEs will be provided by SOC and/ or PT:

- Overall summary of treatment emergent adverse events
- Treatment emergent adverse events
- Treatment emergent adverse events by maximum severity
- Treatment emergent adverse events grade 3 or higher
- Treatment emergent adverse events by relationship to study drug
- Serious treatment emergent adverse events
- Treatment emergent adverse events that led to dose reduction
- Treatment emergent adverse events that led to permanent discontinuation of study drug

All AEs, including treatment emergent events, will be included in listings by subject.

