9.3 ADVERSE EVENTS REPORTING PROCEDURES

The following AEs will be reported and monitored for this study:

- Peripheral Neuropathy (all grades)
- All Grade 3 and 4 AEs
- Any AEs resulting in a missed dose, dose reduction, or treatment discontinuation
- All SAEs

AEs (eg, any new event or worsening in severity or frequency of a pre-existing condition or laboratory finding) with an onset date after the subject signs consent for study participation must be promptly documented on the AE CRF. Details of the event must include severity, relationship to study drug, duration, action taken, and outcome. SAEs will be recorded on

the AE CRF *and* on the SAE reporting form (see [Section 9.5](#), Serious Adverse Event Reporting and Documentation Requirements).

AEs will be collected from the time the subject signs informed consent through 30 days following the last dose of study drugs, or initiation of a new anti-cancer therapy. In addition, the Investigator should report any AE (per instructions described above) that may occur after this time period that is believed to have a reasonable possibility of being associated with study drug.

All AEs that are considered related to study drug must be followed to resolution or stabilization if improvement is not expected. AEs which completely resolve and then recur should be recorded as a new AE. For subjects who complete the end-of-treatment visit less than 30 days following their last dose of protocol-defined therapy, a follow up of ongoing AEs should be attempted by telephone, and documented in the subject's source file.

AEs continuing at 30 days after the last dose should have a comment in the source by the Investigator that the event has stabilized or is not expected to improve.

The Principal Investigator is responsible for evaluating all AEs, obtaining supporting documents, and determining that documentation of the event is adequate. AEs will be assigned a severity grade using the NCI-CTCAE grading scale Version 3.0. Any laboratory finding requiring a therapeutic intervention should also be considered as an AE and reported accordingly.

The Principal Investigator may delegate these duties to Sub-Investigators and must assure that these Sub-Investigators are qualified to perform these duties under the supervision of the Principal Investigator and that they are listed on the Form FDA 1572 or Canadian Qualified Investigator Undertaking Form (QIU).

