10.4 STATISTICAL METHODS

10.4.1 SAFETY ANALYSIS

Safety and tolerability will be assessed by clinical review of all relevant parameters associated with (1) peripheral neuropathy (all Grades) (2) all reported Grade 3 and 4 AEs, (3) Grades 1–4 AEs resulting in a missed carfilzomib dose, dose delay or discontinuation, and (4) reported SAEs.

Treatment-emergent AEs are defined as AEs that start on or after the first day study treatment is administered and within 30 days of the last administration of study treatment.

AEs will be summarized by the number and percentage of subjects who experienced the event, according to system organ class and preferred term. A subject reporting multiple cases of the same AE will be counted once within each system organ class and similarly counted once within each preferred term. Unless otherwise specified, the denominator for these calculations will be based on the number of subjects in each disease cohort (solid tumor or MM) who receive at least 1 administration of carfilzomib on the extended study, irrespective of the total number of doses or treatment cycles administered. These conventions will be appropriately modified to calculate AE incidence rates separately for each cycle that study therapy is administered. AE incidence rates may also be calculated based on other measures of subject exposure (eg, total number of treatment cycles administered). AEs will also be summarized by NCI-CTCAE Version 3.0 severity grade and by relationship to each study drug. For AEs not adequately addressed by the NCI-CTCAE, the severity grading described in [Section 9.1](#) may be used (see [Table 3](#)). Additional summaries may also be provided for SAEs, and events resulting in the permanent discontinuation of therapy. Summaries will be provided by disease cohort. All AEs will be included in individual subject listings.

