3 ANALYSIS ENDPOINTS

3.1 Primary Endpoints - Safety

- Reported peripheral neuropathy AEs (All Grades)
- Reported Grades 3 and 4 AEs
- SAEs
- Grade 1 through Grade 4 AEs leading to a missed carfilzomib dose or a carfilzomib dose reduction, or discontinuation

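### Drug-related adverse events reported with onset more than 30 days after the last dose meet the primary safety endpoint wording but enter none of the listed SAP tables; a separate, flagged count would close the gap

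*SAP*

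**What the plan says.** **Collection.** Protocol 9.3 collects adverse events from consent "through 30 days following the last dose of study drugs, or initiation of a new anti-cancer therapy". It then says that sites should also send in an event of the listed types "that may occur after this time period that is believed to have a reasonable possibility of being associated with study drug". No end date is given for this later reporting. The types meant are those listed at the start of 9.3: neuropathy of any grade, Grade 3 and 4 events, serious events, and events leading to a missed dose, dose reduction or discontinuation.

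**Endpoints.** Protocol 10.2.1 and SAP 3.1 give the primary endpoints without a time window, for example "Reported Grades 3 and 4 AEs". The opening of SAP 7.6 likewise directs the analysis at all reported events of these kinds.

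**Tabulation.** Protocol 10.4.1 defines treatment-emergent events as "AEs that start on or after the first day study treatment is administered and within 30 days of the last administration of study treatment". SAP 7.6.1 uses the same limit ("and within 30 days of the last infusion of study treatment"). Neither makes an exception for related events. SAP 7.6.1 then names eight tables, each restricted to treatment-emergent events, and states that by-subject listings will cover all adverse events.

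**The concern.** The rule for what sites report and the rule for what the tables count stop at different points, and the primary endpoint wording follows the reporting rule. An investigator who reports a related serious event that began six weeks after the last dose has done what Protocol 9.3 asks. The event satisfies the endpoint as written, yet the table of serious events would not include it.

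Safety is the primary endpoint, and the results will be read mainly from the tables. A listing shows that an event happened but gives no count, no percentage and no summary by grade or relationship. For an uncommon serious event, a reader may draw different conclusions from a table showing none and a table showing one.

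**Working it through.** The documents give no power, error-rate or late-event figure to reproduce. The check is a comparison of rules, followed by an illustration of size.

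**1. Follow one event through the plan.** Take a Grade 3 event judged possibly related, with onset 31 days after the last dose.
- Protocol 9.3: routine collection has ended, but the event is of a listed type and related, so the investigator should report it.
- Protocol 10.2.1, SAP 3.1 and SAP 7.6: it is a reported Grade 3 event, so it meets the endpoint.
- Protocol 10.4.1 and SAP 7.6.1: onset is not "within 30 days of the last administration of study treatment", so it is not treatment-emergent.
- SAP 7.6.1 tables: overall summary; all events; by maximum severity; Grade 3 or higher; by relationship; serious; leading to dose reduction; leading to permanent discontinuation. All 8 of 8 are restricted to treatment-emergent events, so this event enters 0 of 8.
- SAP 7.6.1 listings: it appears there.

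Some prose in SAP 7.6.1 speaks of summarizing adverse events without the restriction, but every named table carries it.

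**2. Which events fall in the gap.** Only events with onset after Day 30. A related event that follows a new anti-cancer therapy but starts within 30 days of the last dose is still treatment-emergent under both definitions. Events leading to a missed or reduced dose would not normally start more than 30 days after the last dose, so that endpoint is essentially unaffected.

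**3. Whether late events will reach the database.** Protocol 9.5 ends serious-event reporting at 30 days after the last dose. Appendix A footnote 5 ends Grade 3 and 4 recording at 30 days or at a new anti-cancer therapy. Neither repeats the later-reporting sentence in 9.3, so capture of late events is itself unclear.

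**4. Illustration of size.** Input from SAP 2.3: about 100 subjects. The late-event rate p is assumed.
- One subject whose only event of a type is late: 1/100 = 1.0 percentage point overall, or 1/25 = 4 points in a disease cohort of 25 (an assumed cohort size).
- Expected number of subjects with an uncounted event = 100p. Chance of at least one = 1 − (1 − p)^100.

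| Assumed p | Expected subjects | Chance of at least one |
|---|---|---|
| 1% | 1 | 63% |
| 2% | 2 | 87% |
| 3% | 3 | 95% |
| 5% | 5 | 99% |

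- For a rare event, the exact (Clopper-Pearson) two-sided 95% upper limit at 0/100 is 1 − 0.025^(1/100) = 3.6%. At 1/100 it solves (1 − p)^100 + 100p(1 − p)^99 = 0.025, giving 5.4%.

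These figures show what one omitted event can do. They do not estimate how often it will happen.

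**The case against.** The 30-day limit is a common convention, and much of the plan runs on it. Protocol 3.4 treats a subject as having completed the study 30 days after the last dose. The end-of-study visit in Protocol 7.7 falls within that time, no later visit is scheduled, and the SAP death count in 7.7.1 uses the same limit. The later-reporting sentence in Protocol 9.3 is a passive safety provision, not a second follow-up period. Nobody is systematically observed after Day 30. Merging spontaneous reports, selected by investigator causality, into all-causality percentages of treated subjects would mix two kinds of data and could bring in events that arose under a later therapy. The analysis is descriptive and no decision rule depends on it.

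Most of this stands, and it is a good reason not to widen the treatment-emergent definition. It does not explain why events that sites are asked to report, and that meet the endpoint as worded, should have no count at all.

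Three stronger readings are tempting and unsupported:
- *That the tables remove the late toxicity of long-term treatment.* The window runs from first dose to 30 days after the last, with no cap on treatment length, so toxicity first appearing after many cycles is fully counted. Only onset after dosing has stopped is affected.
- *That the SAP departs from the protocol's definition.* Both use the same limit. The mismatch is between that shared definition and the reporting rule and endpoint wording.
- *That late events are lost, or that sites are strictly obliged to send them.* They stay in the listings, and 9.3 says should, for the listed types only.

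**Conclusion.** The gap is real but modest. As the SAP stands, a reported related event starting more than 30 days after the last dose meets three of the four primary endpoints as worded (Grade 3 and 4, neuropathy, serious) and is counted in no named table. Relative to that wording, the omission can only lower a count. How much is unknown: the documents give no late-event rate, capture is passive, and Protocol 9.5 and Appendix A leave it unclear whether all such events would be recorded. The 1-point effect per subject assumes about 100 treated subjects and a subject with no earlier event of the same type. A reader might infer that the primary percentages are materially biased; the documents do not support that. This is an inexpensive improvement in reporting, and the study's conclusions do not hinge on it.

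**What to change.** Keep the 30-day definition and the eight tables unchanged. Add one table, or a separate row, to SAP 7.6.1:

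- Number and percentage of subjects in the Safety population, by disease cohort and overall, with an adverse event starting more than 30 days after the last dose that the investigator judged possibly or probably related.
- Separate lines for Grade 3 and 4, serious, and peripheral neuropathy events. SAP 7.6.1 names no dedicated neuropathy table, so this line needs to be written in explicitly.
- A flag for onset after the start of a new anti-cancer therapy.
- A footnote that ascertainment after Day 30 is passive, so the count is a minimum and not an incidence rate.

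In the protocol, reconcile the 30-day stops in 9.5 and Appendix A footnote 5 with the later-reporting sentence in 9.3, so that sites know whether late related serious and Grade 3 and 4 events are to be recorded.

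The cost is a sentence in the SAP, one short table or row, and a clarification in two places in the protocol. The data are already asked for under 9.3, so no new collection is needed. The downside is that a reader may take a passively collected count for a rate, which the footnote is there to prevent.

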7.6.2 Concomitant Medications

Concomitant chemotherapies will be collected and coded using WHODDE version March 1, 2010. All chemotherapy agents will be listed individually and summarized by anatomical therapeutic class and generic name.

7.7 Efficacy Analyses

The efficacy analyses will be performed by disease cohort and will be based on investigator's assessment recorded on the CRF page.

All efficacy analyses will be based on the FAS population.

7.7.1 Overall Survival (OS)

Duration of OS is defined as the days from the start of treatment (initial study) to death due to any cause. For subjects who are alive at the time of the data cut-off, duration of OS will be censored as of the date the subject was last known to be alive.

Since the subjects will be followed up till 30 days after administration of last dose of study drug only per protocol, OS will be calculated and presented in a listing, no Kaplan-Meier estimates will be provided. Number and percentage of subjects who died within 30 days after administration of last dose of study drug will be calculated and death reason will be summarized.

7.7.2 Progression Free Survival (PFS)

PFS is defined as number of days between start of treatment and first evidence of documented disease progression or death (due to any cause), whichever occurs first. Disease progression will be determined by the local investigator for regimens with the same baseline using the International Uniform Response Criteria ([Durie et al. 2006, with corrections](#)) (IMWG-URC) for multiple myeloma subjects and RECIST criteria ([Therasse et al. 2000](#)) for solid tumor subjects. PFS will be re-calculated whenever the baseline is reset due to addition of new anti-cancer therapy or increase of carfilzomib dose/frequency:

- 1) For regimens that continue from initial study without baseline being reset, if subjects didn't progress before PX-171-010, then PFS for the period from initial study to PX-171-010 study will be calculated as Disease Progression /Death Date – Date of first dose in initial study + 1 day, and PFS for the period of PX-171-010 study only will be calculated as Disease Progression /Death Date – Date of first dose in PX-171-010 + 1 day.
- 2) For regimens that start in PX-171-010 study with baseline being reset from initial study or previous regimens, PFS will be calculated as Disease Progression /Death Date –

Date of first dose in the first regimen among the regimens with common baseline + 1 day.

PFS will be right-censored for subjects who met one of the following conditions: 1) no baseline disease assessments or any post-baseline assessments, 2) alive and does not have documentation of disease progression before a data analysis cutoff date. The PFS censoring rules are described in Table 1.

Table 1. Censoring Rules for PFS Analysis

Situation	Date of Progression or Censoring	Outcome
No baseline disease assessments or any post-baseline assessments	Date of first dose	Censored
Alive and without documentation of disease progression	Date of last disease assessment	Censored
Death or disease progression between planned disease assessments	Date of death or first disease assessment showing disease progression, whichever occurs first	Progressed
Death or PD immediately after more than 1 consecutively missed disease assessment visit*	Date of last disease assessment before the first missed visit	Censored
Death before first disease assessment	Date of death	Progressed

* If death or PD is more than 168 days after previous disease assessment, or the first dosing date if there is no previous disease assessment.

The number and percentage of subjects with events, the number and percentage of subjects censored will be calculated for each disease cohort (MM, solid tumor) by regimen. The denominator for each regimen will be subjects who had the regimen.

Kaplan-Meier method will be used to estimate the distribution of PFS. The 25%, 50% and 75% KM quartiles will be provided along with a two-sided 95% confidence interval ([Klein and Moeschberger, 1997](#)).

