10.4.2 DISEASE RESPONSE ANALYSIS

The analysis of disease response will be based on the FAS populations defined in [Section 10.3.2](#). The assessment of disease response will be based on duration of OS, PFS, and TTP. For patients previously enrolled in PX-171-008, response may be first noted in PX-171-010. Durations will be calculated from the date of disease response documented in the subjects' prior carfilzomib protocol, or in PX-171-010 for subjects previously enrolled in PX-171-008, to the first documentation of the endpoint's occurrence in the extended trial.

Depending on the completeness of the available follow-up data, analysis of each endpoint will be performed based on the Kaplan-Meier method. The date of progression will be determined using the progression criteria described in [Appendix D–E](#). The date of censoring for subjects who end the study without documented progression will correspond to the date the last disease assessment was performed. Analysis will be performed separately by disease cohort (MM or solid tumor).

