5.5 Baseline

If subjects had not received other anti-cancer therapies and not reached progressive disease when they enrolled in study 010, baseline disease assessments from the initial study will be used for baseline values for determining response and progression unless no prior assessments were collected (eg, PX-171-008). For those subjects who didn't have baseline collected in prior study, tumor assessments will be conducted at the time of screening for the current study using the appropriate method. And for those who received other anti-cancer therapies and/or progressive disease when they enrolled in study 010, baseline values from current study will be used.

During the study, the addition of certain approved agents with known antitumor activity or increase of carfilzomib dose and/or frequency is permitted if there is concern for disease progression and per Investigator discretion in consultation with the Onyx Medical Monitor. If it happens, measurements at the time of addition of new agents will be used as new baseline.

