7.7.3 Time to Progression (TTP)

TTP is defined as number of days between start of treatment to the first documentation of disease progression. TTP will be re-calculated whenever the baseline is reset due to addition of new anti-cancer therapy or increase of carfilzomib dose/frequency:

- 1) For regimens that continue from initial study without baseline being reset, if subjects didn't progress before PX-171-010, then TTP for the period from initial study to PX-171-010 study will be calculated as Date of Disease Progression – Date of first dose in initial study + 1 day, and TTP for the period of PX-171-010 study only will be calculated as Date of Disease Progression – Date of first dose in PX-171-010 + 1 day.
- 2) For regimens that start in PX-171-010 study with baseline being reset from initial study or previous regimens, TTP will be calculated as Date of Disease Progression – Date of first dose in the first regimen among the regimens with common baseline + 1 day. The same censoring rules, except for death, as in analysis of PFS ([Section 7.7.2](#)) will be applied in calculation of TTP. Subjects who die before disease progression will be censored at death date.

The number and percentage of subjects with events, the number and percentage of subjects censored will be calculated. Kaplan-Meier method will be used to estimate the distribution of TTP for each disease cohort by regimens. The 25%, 50% and 75% KM quartiles will be provided along with a two-sided 95% confidence interval ([Klein and Moeschberger, 1997](#)).

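### Read literally, rule 1 of SAP 7.7.2 and 7.7.3 starts the combined PFS and TTP clock of unchanged PX-171-008 rollovers at first parent-study dose, before their disease baseline exists

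*SAP*

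**What the plan says.** SAP 7.7.2 gives two rules for the PFS time origin, and 7.7.3 repeats them for TTP.

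- **Rule 1** applies "For regimens that continue from initial study without baseline being reset", provided the subject had not progressed before entering PX-171-010. It yields two durations. The combined one is "Disease Progression /Death Date – Date of first dose in initial study + 1 day". The second, introduced by "PFS for the period of PX-171-010 study only will be calculated as", runs from first dose in PX-171-010. For TTP the combined wording is "TTP for the period from initial study to PX-171-010 study will be calculated", again from first dose in the initial study.
- **Rule 2** applies "For regimens that start in PX-171-010 study with baseline being reset from initial study or previous regimens", and counts from first dose of the first regimen that shares the new baseline.

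The lead-in to the two rules names the occasions for a reset: "PFS will be re-calculated whenever the baseline is reset due to addition of new anti-cancer therapy or increase of carfilzomib dose/frequency".

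The baseline is defined elsewhere. SAP 5.5 uses the initial study's baseline for subjects who have neither progressed nor had other anti-cancer therapy, "unless no prior assessments were collected (eg, PX-171-008" being the example given. For those subjects SAP 3.2 and 5.5 make the PX-171-010 screening assessment the baseline for response and progression.

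Protocol 10.4.2 measures durations from the date of response in the prior protocol, "or in PX-171-010 for subjects previously enrolled in PX-171-008".

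**The concern.** A time-to-progression clock should not start before the measurement against which progression is judged. For a PX-171-008 subject who continues on the same regimen, the SAP's baseline text and its clock text come apart: the baseline is PX-171-010 screening, while rule 1 starts the combined clock at first dose in PX-171-008.

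Two things follow for that duration. All time on PX-171-008, plus any gap before PX-171-010, is credited as progression-free although no assessment from that time was collected. And tumour growth during that time cannot become an event: Protocol Appendix E judges solid-tumour progression against the smallest sum recorded since treatment started, and the first recorded sum for these subjects is the screening one, so earlier growth is absorbed into the reference.

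Rule 1's own condition, no progression before PX-171-010, cannot be verified for these subjects from collected assessments. What is at stake is whether the combined PFS and TTP in the solid-tumour cohort mean the same thing for all the subjects in them.

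**Working it through.** **Step 1: which rule applies.** Take a PX-171-008 subject who rolls over at the same dose and frequency, as Protocol 1.5 and 6.2.1 provide.

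| Test | Rule 1 | Rule 2 |
|---|---|---|
| Where the regimen begins | Continues from the initial study: fits | Starts in PX-171-010: does not fit |
| Baseline status | Not reset: fits, since this is a first baseline | Reset from the initial study or an earlier regimen: there was no baseline to reset |
| Listed reset occasion | None needed | Added therapy, or more carfilzomib: neither occurred |

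On the wording, rule 1 applies. A PX-171-008 subject who later has an agent added or carfilzomib increased moves to rule 2 for the new regimen, and the problem does not arise there.

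**Step 2: size of the shift.** The documents give no figure that depends on this definition, so there is nothing to reproduce. From the SAP formulas:

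- combined duration = event date − first parent dose + 1
- PX-171-010-only duration = event date − first PX-171-010 dose + 1
- difference = first PX-171-010 dose − first parent dose = parent treatment span + gap

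Inputs: maximum treatment in the parent studies ranges from 1 to 18 cycles (Protocol 1.4); the parent study must have been completed within 90 days before first PX-171-010 dose (Protocol 4.1). The documents give neither treatment length nor cycle length for PX-171-008. I assume 28-day cycles and take completion to be the end of the last cycle.

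- Lower end: 1 × 28 + 0 = 28 days
- Intermediate illustration: 4 × 28 + 30 = 142 days
- Upper end: 18 × 28 + 90 = 504 + 90 = 594 days

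**Step 3: one subject.** Suppose progression is documented 84 days after first PX-171-010 dose. The PX-171-010-only PFS is 84 + 1 = 85 days in every case.

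| Parent cycles, gap | Combined PFS under rule 1 |
|---|---|
| 1 cycle, no gap | 84 + 28 + 1 = 113 days |
| 4 cycles, 30 days | 84 + 142 + 1 = 227 days |
| 18 cycles, 90 days | 84 + 594 + 1 = 679 days |

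TTP shifts by the same amounts. The PX-171-010-only durations shift by 0 days.

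**Step 4: how many subjects.** PX-171-008 plans 15 subjects, all with advanced solid tumours (Protocol 1.3). How many roll over, and how large the solid-tumour cohort is, are not stated. The effect on a cohort median therefore cannot be calculated.

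**The case against.** **Rule 2 may already cover these subjects.** The reset occasions listed in 7.7.2 are not complete: SAP 5.5 also moves the baseline to PX-171-010 for subjects who enter with progressive disease, which is not on that list. A reset from the initial study might then be stretched to PX-171-008. This has some force, and two programmers could choose differently. But rule 2 speaks of regimens that start in PX-171-010 and of a baseline that is reset, and neither describes an unchanged rollover with a first baseline. The ambiguity itself needs settling.

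**Rule 1's condition cannot be checked, so rule 1 may not apply.** In that case the text leaves the combined duration undefined, which also needs a sentence.

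**The full analysis set may remove them.** SAP 4.2 excludes subjects who lack baseline data where an analysis needs it. But SAP 3.2 names screening as their baseline, so they do not lack one. The other exclusion removes only those PX-171-008 subjects without post-baseline data, which implies that the rest stay in.

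**Delayed entry would deal with it.** Entering these subjects into the risk set at first PX-171-010 dose would stop parent time from counting as observed progression-free time. It would not repair an origin that precedes the progression reference, and the SAP specifies only Kaplan-Meier estimation without it.

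**Stronger readings that do not stand.** A reader might infer that solid-tumour PFS and TTP are biased upward as a whole. The documents do not support that: rule 1 also gives an aligned PX-171-010-only duration, and how the combined cohort estimate would move once these subjects are left out depends on the other subjects' parent-study time. A reader might also infer that tumours were never evaluated in PX-171-008; the documents show only that measurements and assessments were not collected under defined criteria. Nor did the SAP simply delete the protocol's PX-171-008 exception. It replaced the protocol's response-date origin for everyone and carried over no exception for these subjects' clock.

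**Conclusion.** The point holds in a limited form. As written, rule 1 gives unchanged PX-171-008 rollovers a combined PFS and TTP that begin before their disease baseline, with parent-study time credited as progression-free and no collected assessment to support it. The excess per subject is the full interval from first parent dose to first PX-171-010 dose, 28 to 594 days as an outer range under the assumptions in the working.

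The effect is confined to the combined initial-study-to-PX-171-010 estimate in the solid-tumour cohort. The SAP does not say whether that or the PX-171-010-only estimate is the main result. Protocol 10.4.2 supports placing these subjects' origin within PX-171-010, but it uses a response date, so it does not by itself establish first dose as the right day.

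These are secondary, descriptive endpoints in a study that tests no hypothesis and whose primary endpoint is safety. The change should be made because the rule is wrong as worded and easily mended, not because a main conclusion depends on it.

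**What to change.** Add one sentence to each of SAP 7.7.2 and 7.7.3: subjects with no disease baseline from the initial study (for example those from PX-171-008) contribute only the PX-171-010 duration, counted from first dose in PX-171-010, and are left out of the combined initial-study-to-PX-171-010 estimate.

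The cost is two sentences of text. The combined estimate loses at most the 15 planned PX-171-008 subjects, whose parent-study time it cannot validly use. They remain in the PX-171-010-only estimate. No new data collection is needed.
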